#### **10.4.1.1 Antitumor activity endpoint definitions**

The following are definitions of the antitumor activity endpoints:

Objective response rate (ORR) is defined as the percentage of participants with a best overall response (BOR) of complete response (CR) or partial response (PR).

Disease control rate (DCR) is defined as the percentage of participants with a BOR of CR, PR, or SD.

Best overall response is defined for each study participant as the best overall tumor response designation, as determined by the investigator according to relevant RECIST criteria, recorded between the first dosing date and the date of documented disease progression or the date of subsequent anticancer therapy (systemic medication, surgery, or radiotherapy for cancer), whichever occurs first. Complete response or PR determinations included in the BOR assessment

must be confirmed by a second scan  $\geq 4$  weeks after the criteria for response are first met. In addition, for a BOR of SD, tumor measurements must have met the criteria for stable disease (SD) at least once after the start of study treatment at a minimum interval of no less than 6 to 8 weeks. Table C in Section 11.9 (Appendix 9) provides the derivation of BOR when confirmation of CR and PR responses are required.

**Duration of response (DOR)** will be calculated for participants who achieve a CR or a PR and is defined as the time in days from the start date of the response to the first date that recurrent or progressive disease is objectively documented. For participants who die without objective disease progression, DOR will be censored on the date of death, regardless of cause. For participants who discontinue early without documented objective progressive disease, DOR will be censored at the date of their last available (scheduled or unscheduled) tumor assessment at which a lack of objective disease progression was determined. A sensitivity analysis will be performed taking into account both objective progressive disease and clinical disease progression, as determined by the investigator, in the calculation of DOR.

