**Progression-free survival (PFS)** is defined as the time in days from first dosing date to the date of the first documented objective disease progression or death due to any cause, whichever occurs first. Participants who died without a documented objective disease progression will be considered to have progressed on the date of their death. Participants who did not progress or die will be censored on the date of their last available (scheduled or unscheduled) tumor assessment. Participants who did not have any on-study tumor assessments and did not die will be censored on the date of their first dose of study treatment. Participants who discontinued early without documented objective disease progression or death will be censored on the date of their last available (scheduled or unscheduled) tumor assessment at which a lack of objective disease progression was determined. Participants who started anti-cancer therapy without a prior documented objective disease progression will be censored on the date of their last available (scheduled or unscheduled) tumor assessment prior to the initiation of the subsequent anti-cancer therapy. A sensitivity analysis will be performed taking into account both objective progressive disease and clinical disease progression, as determined by the investigator, in the calculation of PFS.

**Overall Survival (OS)** is defined for all participants in the study as the time in days from the date of first dosing to the date of death from any cause. Participants will be followed up to ascertain their survival status at the SFU Visit (within 30 days after their final dose of study treatment) and at the Final Visit (3 months after their final dose of study treatment); they will not be followed up beyond this time point. For participants who discontinued early from the study or discontinued study treatment due to disease progression and were not known to have died, OS will be censored on the date of last contact.

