### Subjective progression

Participants requiring discontinuation of treatment without objective evidence of disease progression should not be reported as progressive disease on tumor assessment eCRFs. This should be indicated on the Study Medication Discontinuation eCRF page as Clinical Progression. Every effort should be made to document progressive disease even after discontinuation of treatment.

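### DOR has no rule for subsequent anticancer therapy, although BOR closes at that therapy and PFS is censored at the last scan before it

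*Protocol*

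**What the plan says.** All three definitions stand in Protocol Section 10.4.1.1.

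- **DOR** is "the time in days from the start date of the response to the first date that recurrent or progressive disease is objectively documented". Two censoring rules follow. The first covers death: "For participants who die without objective disease progression, DOR will be censored on the date of death, regardless of cause". The second covers early discontinuation without documented objective progression, and its core reads: "DOR will be censored at the date of their last available (scheduled or unscheduled) tumor assessment at which a lack of objective disease progression". Clinical progression enters only through a sensitivity analysis. Subsequent anticancer therapy is not mentioned.
- **BOR** counts only assessments "recorded between the first dosing date and the date of documented disease progression or the date of subsequent anticancer therapy", whichever is first, and spells out what such therapy covers: "systemic medication, surgery, or radiotherapy for cancer".
- **PFS** has an early-discontinuation rule worded almost like the one for DOR, and then a further one: "Participants who started anti-cancer therapy without a prior documented objective disease progression will be censored on the date of their last available" assessment before that therapy began. The term is not defined there.

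Scans after stopping are foreseen. The schedules of activities (Tables 1-4 to 1-8) include a tumor assessment at the Safety Follow-Up (SFU) Visit, within 30 days of the last dose. It is waived only if the participant withdrew for progression or was scanned within the previous 42 days. Appendix 9, under Subjective progression, adds: "Every effort should be made to document progressive disease even after discontinuation of treatment".

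**The concern.** The three endpoints describe the same participant's tumor course and should stop at the same place when another treatment takes over. BOR and PFS do; DOR does not. If the text is followed literally, a scan taken under the next treatment either supplies the DOR event or moves the DOR censoring date later. Time during which another treatment may be holding the response is then added to a response first recorded on UCB6114, and DOR and PFS for the same person can contradict each other.

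At stake are the Kaplan-Meier DOR estimates and timepoint rates promised in Section 10.4.1.2 and their consistency with PFS and BOR. DOR is exploratory in Parts A, A1, B and C (Tables 3-1 and 3-2) and secondary in Parts D to G (Table 3-3). Section 10.4.1 says the primary antitumor analysis of the expansion parts will be the same as the exploratory one in the escalation parts, so the definitions can be expected to carry over.

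**Working it through.** The protocol states no figure for DOR, so there is none to reproduce. The check sets the rules side by side and applies them to a timeline built from the protocol's own schedule.

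**1. The rules compared**

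| Situation | BOR | DOR | PFS |
|---|---|---|---|
| Objective progression | window closes | event | event |
| Early stop, no progression | no separate rule | last available progression-free scan | last available progression-free scan |
| New anticancer therapy, no progression | window closes | **no rule** | last scan before the therapy |

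PFS carries both of the last two rules. The protocol therefore does not treat the discontinuation rule as covering new therapy, and in DOR that rule is not limited to scans before the therapy.

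**2. Inputs (Part A schedule)**

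- First dose is day 1, with 28-day cycles and doses on Days 1 and 15.
- Scans fall on Days 21 to 28 of even cycles (Section 9.6.1; Table 1-4). The late end of the window is day 56 in Cycle 2 and 3 × 28 + 28 = 112 in Cycle 4.
- Partial response is seen on day 56 and confirmed on day 112, meeting the 4-week minimum.
- The last dose is Cycle 6 Day 15: 5 × 28 + 15 = day 155. The participant stops for toxicity or choice, without progression.
- New systemic therapy starts about day 160 (assumed), just before the Cycle 6 scan window opens on day 161.
- The SFU scan is at the 30-day limit: 155 + 30 = day 185. The previous scan was 185 − 112 = 73 days earlier, more than 42, so the scan is required.

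**3. Results**

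- PFS is censored at day 112: 112 − 1 = **111 days**.
- DOR as written runs to day 185: 185 − 56 = **129 days**. It is an event if that scan shows progression and a censoring if not.
- DOR under the PFS rule is 112 − 56 = **56 days**.

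Durations are date differences. Counting both end days adds one to each and changes no comparison.

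**4. When DOR exceeds PFS**

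Let R be the response day, S the last scan before new therapy and E the later scan. DOR = E − R and PFS = S − 1, so DOR exceeds PFS only if E − S > R − 1. In the case above, 73 > 55. Other last-dose days, with the SFU scan 30 days later:

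| R | S | Last dose | E | E − S | DOR | PFS |
|---|---|---|---|---|---|---|
| 56 | 112 | 113 | 143 | 31 (scan not required) | 87 | 111 |
| 56 | 112 | 127 | 157 | 45 | 101 | 111 |
| 56 | 112 | 141 | 171 | 59 | 115 | 111 |
| 49 | 105 | 127 | 157 | 52 | 108 | 104 |
| 49 | 105 | 141 | 171 | 66 | 122 | 104 |
| 49 | 105 | 155 | 185 | 80 | 136 | 104 |

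Among these compliant timelines and the case in step 3, the excess over PFS runs from 115 − 111 = 4 to 136 − 104 = 32 days. It is absent when the participant stops soon after a scan. DOR running past the PFS censoring date needs only one scan after the new therapy starts.

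**5. After the change**

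Every row gives DOR = S − R = 56 days. For participants handled by the new-therapy rule, DOR equals PFS minus the time to response and cannot exceed PFS.

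**The case against.** The strongest reply is that little is left uncovered. Section 7.1.3 makes study treatment stop before another agent begins, so these participants fall under DOR's discontinuation rule. If the last scan was within 42 days of the SFU Visit and no extra scan is done, DOR and PFS are censored on the same date. No imaging is scheduled after SFU, and the Final Visit at 3 months may be a phone call. The Appendix 9 instruction concerns participants recorded as clinical progression and sets no scan schedule. DOR is only summarized descriptively, and full methodology is left to the SAPs.

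Most of this stands as a limit on size. It does not remove the gap: the discontinuation rule uses the last available scan, including one taken under the next treatment, and the SFU scan is mandatory once more than 42 days have passed. Nor is this detail merely deferred. The protocol fixes the DOR event, two censoring rules and a sensitivity analysis, and gives the missing rule for PFS. A SAP that follows the text inherits the inconsistency, and one that adds the rule departs from the protocol.

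Three stronger readings are tempting but not supported. A reader might infer that DOR always exceeds PFS; the table shows it need not. A reader might infer that responses produced by the next treatment are credited to UCB6114; the BOR window closes at that treatment, so only an existing response can be lengthened. A reader might infer that many months on the next systemic treatment enter DOR; planned imaging ends at SFU, so this would need unscheduled scans.

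**Conclusion.** Wrong as written, with a modest effect. BOR and PFS recognise subsequent anticancer therapy and DOR does not, so DOR can run on under another treatment after PFS has been censored. In the schedule-compliant case it is 129 days against PFS of 111, and 56 under the PFS rule. That rests on new therapy starting before the SFU scan and on a gap of more than 42 days since the previous scan (or an unscheduled scan). The protocol gives no basis for how often this will happen.

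No error rate or sample size is affected. One case could still matter because responders will be few: at an assumed response rate of 10% to 30%, an expansion part of 15 has about 1.5 to 4.5 responders (0.10 × 15 to 0.30 × 15).

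Two points remain open in the text and are not needed for the conclusion. Palliative radiotherapy is permitted in Parts A1, B and C (Sections 6.5.2 to 6.5.4) while treatment and scans continue, so the short follow-up would not bound the run-on there; BOR names radiotherapy as anticancer therapy, but PFS does not define the term. And for a participant who starts new therapy and then dies without progression, DOR is censored at death, while the protocol does not rank the PFS death and new-therapy rules.

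**What to change.** Add to the DOR definition the rule already used for PFS: responders who start subsequent anticancer therapy without prior documented objective progression are censored at their last tumor assessment before that therapy starts. Use one definition of subsequent anticancer therapy for BOR, DOR and PFS, and state whether permitted palliative radiotherapy counts.

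The cost is one sentence and one shared definition. The therapy start date is already needed for BOR and PFS, so no new data are collected. The downside is that DOR may be slightly shorter or more often censored. The planned amendment for Parts D to G is a natural place for the change.

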#### **10.4.1.2 Analysis of the antitumor activity endpoints**

Unless specified otherwise, the antitumor activity analyses will be conducted using the PPS with sensitivity analyses conducted using the SS (see Section 10.1). The results of these analyses will be presented for each study part.

Tumor response data, as determined using RECIST criteria, will be tabulated. Tabulations will be presented by dose level for each cohort.

Exploratory analyses of selected antitumor activity endpoints may be performed based on subgroups of participants in the SS. Data permitting, the subgroups will be defined based on participant, disease, and treatment history information (eg, extent of prior anti-cancer therapy).

For the antitumor activity endpoints ORR and DCR, the proportion of participants achieving response, and, if data allow, the exact 95% confidence interval for this proportion will be estimated using the Clopper-Pearson method and presented for the response rates.

Duration of response, PFS and OS will be summarized descriptively using the Kaplan-Meier method with 95% CIs calculated using Greenwood's formula. Duration of response and PFS rates at specific timepoints (3 months, 6 months, 12 months, etc.) will also be derived from the Kaplan-Meier estimation and presented together with associated 95% CIs.

A full discussion of statistical methodology will be provided in the SAPs for each module.

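### Duration of response is censored when a responder dies without progression, while PFS counts the same death as an event, and no reason is given for the difference

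*Protocol*

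**What the plan says.** All the relevant rules are in Protocol Section 10.4.1.1 and are applied in Section 10.4.1.2.

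- **DOR event.** DOR runs from the start of response "to the first date that recurrent or progressive disease is objectively documented". Death is not an event.
- **DOR, death first.** "For participants who die without objective disease progression, DOR will be censored on the date of death, regardless of cause".
- **DOR, early discontinuation without progression.** "DOR will be censored at the date of their last available (scheduled or unscheduled) tumor assessment".
- **DOR sensitivity analysis.** One is planned, "taking into account both objective progressive disease and clinical disease progression, as determined by the investigator, in the calculation of DOR". It does not add death.
- **PFS event.** PFS runs to the "first documented objective disease progression or death due to any cause, whichever occurs first". The text repeats the rule for deaths: "Participants who died without a documented objective disease progression will be considered to have progressed on the date of their death".
- **Estimator.** "Duration of response, PFS and OS will be summarized descriptively using the Kaplan-Meier method with 95% CIs calculated using Greenwood's formula". In addition, "Duration of response and PFS rates at specific timepoints (3 months, 6 months, 12 months, etc.) will also be derived from the Kaplan-Meier estimation".

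The objectives tables (Tables 3-1 to 3-3) list DOR as exploratory in Parts A, A1, B and C and as secondary in Parts D to G.

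**The concern.** A responder who dies is no longer in response. Censoring at death nevertheless tells the Kaplan-Meier estimator that this person left the risk set with progression still to come, at the same rate as the responders who remain. The curve then answers how long response would last if nobody died first. Most readers of a DOR median will take it as how long responders stayed alive and in response.

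The PFS paragraph of the same section treats the same participant on the same date the other way, and both endpoints go through the same estimator and landmark times. A reader who sets the two results side by side will be comparing a progression-only curve with a progression-or-death curve without being told so.

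What is at stake is the meaning of a reported secondary or exploratory result. With few responders the choice can matter. Section 10.8.2 plans 15 to 30 participants per expansion module. At an illustrative 20% response rate that is 15 × 0.20 = 3 to 30 × 0.20 = 6 responders, so the status of one death can move or remove the median.

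**Working it through.** The protocol states no figure for DOR (no expected median, event count or precision), so there is nothing to reproduce. Direction and size can be checked separately.

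**Direction, without distributional assumptions.** Take responders to whom the death rule applies. Under the protocol rule and under a progression-or-death rule each of them has the same date, namely the date of death. Only the status differs. The numbers at risk are therefore identical at every time. The progression-or-death curve is the death-censored curve multiplied by an extra factor (1 − d/n) at each death time, where d is the number of deaths and n the number at risk. Each factor is at most 1, so the death-censored curve can only be equal or higher.

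**Size, under a simple model.** The inputs are assumptions, because the documents give none:

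- constant, independent hazards of progression (L_p) and of death without progression (L_d);
- a median to progression or death of 6.0 months, so L_p + L_d = ln 2 / 6.0;
- a share of first events that are deaths, s = L_d / (L_p + L_d), from 0% to 30%.

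With deaths as events the median is ln 2 / (L_p + L_d) = 6.0 months. With deaths censored, Kaplan-Meier estimates ln 2 / L_p = 6.0 / (1 − s). The 12-month rate goes from 0.25 to 0.25^(1 − s).

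| Share s | Death-censored median (months) | Ratio 1/(1 − s) | 12-month rate, deaths censored | 12-month rate, deaths as events |
|---|---|---|---|---|
| 0% | 6.0 | 1.00 | 25.0% | 25.0% |
| 5% | 6.0/0.95 = 6.32 | 1.05 | 26.8% | 25.0% |
| 10% | 6.0/0.90 = 6.67 | 1.11 | 28.7% | 25.0% |
| 20% | 6.0/0.80 = 7.50 | 1.25 | 33.0% | 25.0% |
| 30% | 6.0/0.70 = 8.57 | 1.43 | 37.9% | 25.0% |

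**A small invented data set.** Ten responders have end times 2, 3, 4, 5, 6, 7, 8, 9, 10 and 12 months. Those at 3, 6 and 9 are deaths without progression and the other seven are progressions. With deaths censored the curve is 0.540 at 7 months and 0.405 at 8, so the median is 8 months. With deaths as events the curve reaches 0.500 at 6 months, so the median is 6 months.

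**Coverage of the sensitivity analysis.** A responder with clinical progression recorded before death becomes an event there. A responder who dies with none recorded remains censored, and so is an event in no DOR analysis that the protocol plans.

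**The case against.** Several points on the other side stand.

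- **A reader might infer that the DOR rule contradicts the PFS definition.** It does not. They are separately defined endpoints, and both rules can be applied to one participant. Censoring deaths follows from a DOR definition that names only progression. What remains is an unexplained difference.
- **A reader might infer that the table shows bias from informative censoring.** It does not. Under independent hazards, Kaplan-Meier with deaths censored correctly estimates time to progression alone. The ratio 1/(1 − s) measures the distance between two definitions. Deaths in advanced cancer may well be informative for progression, but the documents give no data from which to size that.
- **A reader might infer that the sensitivity analysis does nothing about deaths.** That is too strong, because it captures those preceded by recorded clinical progression.
- **The impact is limited.** DOR is descriptive. Deaths appear elsewhere: as events in PFS and OS, in the tabulation of fatal adverse events, and in the listing of on-study deaths (Section 10.3.1). Survival is followed only to 3 months after the final dose, which limits how many such deaths can be seen. Not all modules may open (Section 4.1), and antitumor assessments for Parts D to G are to be described in an amendment (Section 9.6).

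These points bound the finding but do not remove it. The definitions in Section 10.4.1.1 are not restricted to particular study parts, so unless amended they carry into Parts D to G. None of the points supplies a reason for treating death differently in the two endpoints.

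**Conclusion.** The point holds as a weakness in an endpoint definition. As written, DOR will be equal to or longer than the time responders are alive and progression-free. Deaths with no prior clinical progression are not events in any DOR analysis that the protocol plans.

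Under constant independent hazards and an assumed 6.0-month median to progression or death, the median would read 6.3 to 8.6 months for death shares of 5% to 30%, an increase of about 5% to 43%. It would be unchanged if no responder dies first. The real share is unknown, so the size is illustrative and only the direction is firm.

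The consequence is confined to the interpretation of a descriptive endpoint. Dose escalation rests on dose-limiting toxicities and safety review, and the expansion sample sizes rest on response rate and practical considerations. DOR enters neither.

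**What to change.** In Section 10.4.1.1, define DOR as the time from first documented response to first objective progression or death from any cause, whichever comes first, and delete the sentence that censors at death. If the progression-only quantity is wanted, keep it at most as a sensitivity analysis under its own label, such as *time from response to progression*.

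Do not simply adopt all PFS rules by cross-reference. PFS also censors at the last assessment before subsequent anticancer therapy, which the DOR paragraph does not mention. Whether DOR should do the same is a separate choice and should be stated as one.

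The change needs no new data, since dates of death are already collected for PFS and OS. Its cost is that the reported DOR may be shorter.

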#### **10.4.1.2 Analysis of the antitumor activity endpoints**

Unless specified otherwise, the antitumor activity analyses will be conducted using the PPS with sensitivity analyses conducted using the SS (see Section 10.1). The results of these analyses will be presented for each study part.

Tumor response data, as determined using RECIST criteria, will be tabulated. Tabulations will be presented by dose level for each cohort.

Exploratory analyses of selected antitumor activity endpoints may be performed based on subgroups of participants in the SS. Data permitting, the subgroups will be defined based on participant, disease, and treatment history information (eg, extent of prior anti-cancer therapy).

For the antitumor activity endpoints ORR and DCR, the proportion of participants achieving response, and, if data allow, the exact 95% confidence interval for this proportion will be estimated using the Clopper-Pearson method and presented for the response rates.

Duration of response, PFS and OS will be summarized descriptively using the Kaplan-Meier method with 95% CIs calculated using Greenwood's formula. Duration of response and PFS rates at specific timepoints (3 months, 6 months, 12 months, etc.) will also be derived from the Kaplan-Meier estimation and presented together with associated 95% CIs.

A full discussion of statistical methodology will be provided in the SAPs for each module.

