**Table 3-3: Objectives and endpoints for the expansion modules in Parts D, E, F, and G**

Objectives	Endpoints
Primary	
To assess preliminary antitumor activity of UCB6114 when administered as monotherapy (Part D and Part E) or in combination with selected SOC regimens (Part F and Part G) according to relevant RECIST criteria	Antitumor activity as indicated by ORR
Secondary	
To characterize the safety profile of UCB6114 as monotherapy or in combination with selected SOC regimens	

• Incidence of TEAEs

• Severity of TEAEs

To document any antitumor activity observed with UCB6114 when administered as monotherapy or in combination with selected SOC regimens	Antitumor activity as indicated by: 

• DCR

• DOR

• PFS

• OS

Tertiary/exploratory	
To explore PD biomarkers of UCB6114 administered as monotherapy or in combination with selected SOC regimens	Change in transcriptional and protein marker levels in blood and tumor tissue by scheduled assessment
To characterize the PK of UCB6114 administered as monotherapy or in combination with selected SOC regimens	UCB6114 concentration by scheduled assessment and dose level
To evaluate the immunogenicity of UCB6114 administered as monotherapy or in combination with selected SOC regimens	ADA (anti-UCB6114 antibody) titer and sample status by scheduled assessment

ADA=antidrug antibody; DCR=disease control rate; DOR=duration of antitumor response; ORR=objective response rate; OS=overall survival; PD=pharmacodynamic(s); PFS=progression-free survival; PK=pharmacokinetic(s); RECIST=Response Evaluation Criteria in Solid Tumors; SOC=standard of care; TEAE=treatment-emergent adverse event

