#### **Per-protocol Set**

The Per-protocol Set (PPS) will include all study participants in the SS who do not have important protocol deviations that may substantially affect antitumor activity. The PPS will be the primary analysis set for the analysis of the exploratory antitumor activity endpoints.

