## **10.4 Planned efficacy/outcome analyses**

### **10.4.1 Analysis of antitumor activity/outcome endpoint**

The analysis of the primary antitumor activity/outcome endpoint in the expansion modules (Parts D, E, F, and G) will be the same as the analysis of the exploratory antitumor activity/outcome endpoints in the dose escalation modules and will be further described, as applicable, in a planned protocol amendment.

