## **10.5 Handling of protocol deviations**

After all data have been verified/coded/entered into a database, a data review will be performed. The purpose of this review will be to check all protocol deviations, define the PPS, and check the quality of the data. The review will also help decide how to manage problems in the participants' data (eg, missing values, withdrawals, dropouts, and protocol deviations). Accepted deviations from theoretical time points will be described in the appropriate documents and included in the Trial Master File. After the pre-analysis review, resolution of all issues, and documentation of all decisions, the database will be locked.

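### Antitumour activity, including the primary ORR of Parts D to G, is analysed first in a Per-protocol Set defined after all data are in, in an open-label study; the all-treated set should come first

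*Protocol*

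**What the plan says.** Protocol Section 10.1 defines the PPS as "all study participants in the SS who do not have important protocol deviations that may substantially affect antitumor activity", and adds: "The PPS will be the primary analysis set for the analysis of the exploratory antitumor activity endpoints". It lists no categories of excluding deviation. Section 10.4.1.2 applies the PPS as the default for every antitumour endpoint: "Unless specified otherwise, the antitumor activity analyses will be conducted using the PPS with sensitivity analyses conducted using the SS (see Section 10.1").

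Section 10.4.1 extends this to the expansion modules. It says that the analysis of their primary antitumour endpoint "will be the same as the analysis of the exploratory antitumor activity/outcome endpoints in the dose escalation modules", and leaves further description to a later amendment. Table 3-3 gives that primary endpoint as "Antitumor activity as indicated by ORR".

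On timing, Section 10.5 says: "After all data have been verified/coded/entered into a database, a data review will be performed". It continues: "The purpose of this review will be to check all protocol deviations, define the PPS, and check the quality of the data". The database is locked after this review and after decisions have been documented. Section 6.3 states that the study is open-label, and Section 10.4.1.1 bases best overall response on the investigator's assessment.

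**The concern.** A single-arm ORR has no control arm to absorb a distorted denominator, so who is counted matters as much as who responds. Here the first-line denominator leaves out treated participants whose deviations are judged likely to affect antitumour activity. That judgement is scheduled for when responses are already recorded and visible, and the protocol text does not require the people making it to be kept unaware of response.

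Participants who are doing badly may be more likely to miss scans or take prohibited treatment. If so, exclusions would fall more often on non-responders and the rate would be pushed up.

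In Parts A, A1, B and C the antitumour endpoints are exploratory and no formal testing is planned, so little turns on this. The weight lies in Parts D to G, where ORR is primary and where Section 4.2 says that the modules replace separate Phase 2 studies.

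**Working it through.** **Inputs.** Expansion sizes of 15 and 30, and the two zero-response statements, come from Section 10.8.2. The exact Clopper-Pearson 95% interval comes from Section 10.4.1.2. The protocol gives no expected number of PPS exclusions, so the numbers below are assumptions shown as a range.

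**Step 1: the plan's own figures.** The chance of no responses in n participants at response rate p is (1 − p)^n.
- n = 15, p = 0.20: 0.8^15 = 0.0352, or 3.52%. The plan states less than 4%.
- n = 30, p = 0.10: 0.9^30 = 0.0424, or 4.24%. The plan states less than 5%.

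Both reproduce. Both are counted over enrolled participants in sequence, not over the PPS.

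**Step 2: effect on ORR of removing non-responders.** ORR = responders / denominator.

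| Treated | Responders | Non-responders excluded (assumed) | ORR | Exact 95% CI |
|---|---|---|---|---|
| 15 | 3 | 0 | 3/15 = 20.0% | 4.3 to 48.1 |
| 15 | 3 | 1 | 3/14 = 21.4% | 4.7 to 50.8 |
| 15 | 3 | 2 | 3/13 = 23.1% | 5.0 to 53.8 |
| 15 | 3 | 3 | 3/12 = 25.0% | 5.5 to 57.2 |
| 30 | 6 | 0 | 6/30 = 20.0% | 7.7 to 38.6 |
| 30 | 6 | 3 | 6/27 = 22.2% | 8.6 to 42.3 |
| 30 | 6 | 6 | 6/24 = 25.0% | 9.8 to 46.7 |

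**Step 3: the other direction.** The PPS rule does not refer to response, so a responder with an important deviation leaves too. Excluding one responder from 3/15 gives 2/14 = 14.3%. The denominator is therefore unstable in both directions, and the upward shift in Step 2 is one possible outcome.

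**Step 4: fit with other sections.** Section 10.8.2 justifies 15 and 30 by counting enrolled participants. Section 10.4.1.1 defines OS for all participants in the study, yet the default in Section 10.4.1.2 analyses it in the PPS. Section 10.4.1.2 also places the exploratory subgroup analyses in the SS, so subgroup counts need not add up to the headline count. An all-treated primary set removes the last two mismatches. It also comes closer to Section 10.8.2 than the PPS does, although the Enrolled Set in Section 10.1 strictly means everyone who signs consent.

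**The case against.** The case for leaving the text alone has several sound parts.

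- **Parts D to G are provisional.** Section 10.1 gives the PPS primary status only for exploratory endpoints. The extension to the primary ORR rests on one sentence in Section 10.4.1, with an amendment to follow, and not all modules may open. This limits the weight of the point. As written, however, that sentence says the analysis will be the same.
- **Exclusion needs an important deviation, not non-response.** Not every missed dose is a deviation: Sections 7.1.4 and 7.4 allow dose holds and COVID-19-related missed doses. This stands, and it is why the direction of bias is plausible rather than shown.
- **The review precedes lock, and an SS analysis is planned.** Any gap between the two sets would therefore be visible. This stands, but the headline figure would still be the PPS one.
- **The analysis plan may list excluding deviations in advance.** It may, and the absence of a list from the protocol is not the complaint. The point is which set the protocol makes primary, and when it is defined.

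Two stronger readings are tempting but not supported.

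- **A reader might infer that the PPS invalidates the zero-response statements in Section 10.8.2.** Substituting 14 for 15 does give 0.8^14 = 4.40%, and 28 for 30 gives 0.9^28 = 5.23%, both above the stated bounds. But Section 10.8.2 makes no such substitution. Its statements count enrolled participants and apply when no responses are seen, and removing non-responders cannot create a response.
- **A reader might infer that PPS exclusions could reverse the decision to expand from 15 to 30.** That decision is taken during the module on observed activity (Table 4-1, Section 10.8.2), and neither place ties it to the PPS. On the timing in Section 10.5 the PPS would not yet exist. The threshold for Parts F and G is also still to be defined, so no reversal can be calculated.

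**Conclusion.** The point holds in a limited form. The protocol makes the PPS the first-line set for antitumour activity, carries that to the primary ORR of Parts D to G, and defines the set when responses are visible in an open-label study. With 15 treated and 3 responders, excluding 1 to 3 non-responders raises ORR by 1.4 to 5.0 percentage points. With 30 treated and 6 responders, excluding 3 to 6 raises it by 2.2 to 5.0 points. These shifts are small beside the width of the intervals, and they rest on assumed counts and on the exclusions being non-responders.

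The consequence lies mainly in Parts D to G and depends on the planned amendment keeping the present wording. DOR is calculated in responders only, so removing non-responders does not change it. The zero-response figures stand.

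**What to change.** In Sections 10.1, 10.4.1 and 10.4.1.2:

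- Make the SS (all treated participants) the primary set for ORR, DCR, PFS and OS, above all for the primary ORR of Parts D to G.
- State that treated participants without a post-baseline tumour assessment stay in the ORR and DCR denominators and count as non-responders. The ORR definition in Section 10.4.1.1 already implies this for ORR within whichever set is used; saying so removes doubt about the set.
- Make the PPS the sensitivity set.

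In Section 10.8.2, and in the expansion rows of Table 4-1, state that the decision to go from 15 to 30 uses all treated participants.

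The cost is wording only, because both analyses are already planned. The headline rate may be slightly lower. The planned amendment for Parts D to G is a natural place for the change.
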